**ANCILLARY STUDIES**

**Study n°1 : DDR1 activity as a predictor of efficacy of regorafenib**

Paraffin-embedded human solid tissue blocks will be sent off at room temperature at the end of the inclusions.

Paraffin-embedded human solid tissue blocks will be returned to the home institution upon completion of ancillary study.

We would like to :

	
 
1. assess the baseline activity of DDR1 in colorectal samples,
 
2. to compare the baseline DDR1 activity to the one of patients (actually those who present some degree of tumor shrinkage) who undergo primarily unplanned hepatectomy and let liver metastases available to study,
 
3. to correlate baseline DDR1 activity to FOLFIRINOX-R efficacy (response rate, PFS, progression-free survival since maintenance therapy onset with regorafenib),
 
4. to correlate DDR1 activity on resected liver metastases to the time to recurrence.
 
5. To proceed to the following additional in vitro and in vivo experiments in order to strengthen the importance of DDR1 inhibition provided by regorafenib:           
 
➤ Test the capacity of regorafenib (1-10nM) to inhibit invasive properties of colorectal tumor cells induced by DDR1 overexpression in collagen matrix in vitro.
 
➤ Test in vivo the capacity of regorafenib treatment (10mg/kg) to block metastatic development induced by DDR1 overexpression in colorectal tumor cells that were transplanted in the spleen of nude mice.
 
➤
 
 
 
 
Actually, with this translational research, we aim to assess DDR1 activity as a predictor of efficacy in mCRC patients treated with a regorafenib-based therapy.
 
Study n°2 : cfDNA monitoring
 
Three EDTA tubes will be collected at baseline, every 8 weeks during treatment and at the end of treatment.
 
Because cfDNA analysis has the capacity to reflect tumor load, it could be used to monitor the efficacy of response of mCRC patients to treatment.
 
We aim to better understand the changes of cfDNA concentration along a regorafenib-based therapy.

STATISTICAL CONSIDERATIONS	
Phase I
 
A minimum of 12 and a maximum of 24 patients will be included. The dose escalation corresponding to a minimum of 3 and a maximum of 6 patients per dose level.
 
A total of 6 patients will be included at the RP2D.
 
Phase II
 
With a one-stage Fleming design, <math>\alpha = 5\%</math>, <math>\beta = 20\%</math>, <math>p_0</math> (the probability of inefficiency maximum) = 35% and <math>p_1</math> (the probability of minimum efficiency) = 50%, it would be necessary to include 65 evaluable patients (69 patients/ 5% non-evaluable patients).
 
The association can be considered sufficiently effective (reject null hypothesis) if there are at least 29 success (48 weeks disease

STATISTICAL CONSIDERATIONS	
control rate = CR / PR / SD) out of 65 evaluable patients, the success rate is significantly greater than 35%. The association can be considered insufficiently effective (rejection of the alternative hypothesis) if there are 28 or less success out of 65 evaluable patients, the success rate is significantly lower than 50%.
 
In total, a maximum of 87 (=18 patients for phase I + 69 patients for phase II including 6 patients treated at the RP2D during the phase I) patients will be included.
 
Analysis population
 
Intent To Treat (ITT) population = all included patients.
 
Per-Protocol (PP) population = all eligible patients (patients with no major violations of the inclusion/exclusion criteria) and evaluable patients (included treated patients with evaluation at 48 weeks or without evaluation at 48 weeks if progressive or dead patient).
 
Safety population = all treated patients who received at least one dose of treatment. All statistical analysis will be performed on ITT population, on PP population for efficacy analysis and on Safety population for safety analysis.

STUDY PERIOD	
 
❖ First inclusion: april 2019
 
❖ Inclusion period: 12 months Phase I + 12 months Phase II
 
❖ End of the inclusion period: march 2021
 
❖ Expected end of study: june 2022
 
❖ Report: september-december 2022
 
❖ Poster/public: phase I (2020), phase II (april 2023 and july 2023)
 

## 1. Background and rationale

### Colorectal cancer

Colorectal cancer (CRC) is a major cause of morbidity and mortality globally. More than 50% of patients can be expected to develop metastatic disease, and most of these patients will require palliative systemic therapy. The primary goal for patients who present with technically resectable liver metastases is definitely cure, with R0 resection as the primary goal. However, any patient with limited liver and/or lung metastases should be considered a candidate for potential secondary resection as there are no criteria that allow physicians to distinguish between those patients for whom purely palliative treatment and those for whom potentially curative treatment is appropriate. Although survival times are slightly shorter for patients who undergo conversion therapy followed by surgery than for patients with initially resectable metastatic disease, they are far better than if resection is not carried out at all (1).

As per ESMO guidelines, first-line therapy commonly involves the doublet (2-CT) regimens of 5-fluorouracil, folinic acid, and either oxaliplatin (FOLFOX) or irinotecan (FOLFIRI). The addition of targeted therapies, such as bevacizumab (a pure anti-angiogenic agent which binds circulating VEGF-A), cetuximab, and panitumumab, to FOLFOX or FOLFIRI may be helpful to some patients in improving tumor response and ultimately overall survival. The cytotoxic triplet (3-CT) FOLFOXIRI with or without bevacizumab may be an option in selected fit and motivated patients when cytoreduction (tumour shrinkage) is needed to undergo conversion therapy (1).

### RAS-mutated (RAS-mut) mCRC

RAS mutations are found in about 50% of mCRC tumors. As recently rephrased by Modest et al. (2) these mutations exclude affected patients from epidermal growth factor receptor (EGFR)-directed therapy. Besides their negative predictive value, RAS mutations may also carry distinct prognostic information. Modest et al. (2) studied the prognosis by RAS status of a total of 1239 mCRC patients from five randomized trials studying 2-CT. Actually, PFS and OS were significantly influenced by molecular subgroups. Multivariate comparison of PFS and OS in patients with mutant tumors versus patients with non-mutated tumors revealed a negative prognostic effect of RAS mutations. Interestingly, the negative prognostic role of these mutations was consistently observed across different treatment regimens (subgroups of irinotecan- and oxaliplatin-treated patients as well as in bevacizumab- and non-bevacizumab-treated patients). Median PFS and OS were 10.3 vs. 9.5 months and 26.9 vs. 21.1 months in RAS-wildtype (and BRAF-wildtype) and RAS-mut patients, respectively

(2).The TRIBE consortium reported that a 3-CT (FOLFOXIRI) combined with bevacizumab provided a significantly longer PFS (the primary end-point of the study) than did the 2-CT FOLFIRI plus bevacizumab (3, 4). In the subgroup of *RAS*- and *BRAF*-wild-type patients, those in the FOLFOXIRI plus bevacizumab group reported a median PFS of 13.7 months (95%CI, 10.1-18.1) compared with 12.2 months (95%CI, 9.5-14.4) in the FOLFIRI plus bevacizumab group (HR 0.85, 95%CI 0.55-1.3) (4). Later on, the same group reported that FOLFOXIRI plus bevacizumab provided a significantly longer overall survival than the FOLFIRI plus bevacizumab group (HR 0.80, 95%CI 0.65-0.98;  $p=0.03$ ) (4). Looking at survival by *RAS* status, Cremolini et al. (4) reported that median OS was 37.1 months (95%CI, 29.7-42.7) in the *RAS*- and *BRAF*-wild-type subgroup compared with 25.6 months (95%CI, 22.4-28.6) in the *RAS*-mut subgroup (HR 1.49, 95%CI, 1.11-1.99). Interestingly, median PFS was 13.7 months (95% CI 10.1-18.1) in the *RAS*-wild-type subgroup treated with FOLFOXIRI plus bevacizumab, while PFS data were not given for the *RAS*-mut patients (4). However, it was possible to estimate median PFS (i.e. 9.4 months) from the Kaplan-Meier curve which was provided for these *RAS*-mut patients (4).

**The median PFS to benchmark in *RAS*-mut mCRC is 9.4 months (with FOLFOXIRI plus bevacizumab)**

### **Regorafenib**

Regorafenib is a small-molecule inhibitor of multiple membrane-bound and intracellular kinases RET, VEGFR 1, 2, 3, c-Kit, PDGFR- $\alpha$ ,  $\beta$ , FGFR1, 2, TIE2, DDR1, DDR2, Trk2A, Eph2A, RAF-1, BRAF, BRAFV600E, SAPK2, PTK5, and Abl. Beyond its well-known antiangiogenic properties, regorafenib has also less-known anti-proliferative activities in human colon cancer cell lines. Interestingly, regorafenib potently inhibits growth of patient-derived CRC xenografts alone and in combination with irinotecan (5-7). Regorafenib is approved for refractory mCRC patients (8), for locally advanced, unresectable or metastatic GIST patients and for HCC patients previously treated with sorafenib. The recommended dose is 160 mg (40 mg  $\times$  4 tablets) orally, once daily for the first 21 days of each 28-day cycle. Two phase III trials demonstrated a significant overall survival benefit for regorafenib over placebo in patients with mCRC who progressed on standard therapies (8, 9). Two phase II trials studied the safety and efficacy profile of regorafenib when combined to chemotherapy in patients with mCRC (10, 11). *In vitro* data indicate that both regorafenib and its metabolite M-2 inhibit glucuronidation mediated by UGT1A1 and UGT1A9 (whereas M-5 only inhibits UGT1A1), hence triggering potential pharmacokinetic interactions. The study

from Schultheis et al. (10) was designed to explore whether addition of regorafenib to FOLFOX or FOLFIRI could be feasible as a treatment of mCRC, in terms of safety and pharmacokinetic interactions of the various drug components of the regimen. Forty-five patients were treated every 2 weeks with 5-fluorouracil 400 mg/m^2 bolus then 2400 mg/m^2 over 46 h, folinic acid 400 mg/m^2, and either oxaliplatin 85 mg/m^2 or irinotecan 180 mg/m^2. On days 4–10, patients received regorafenib 160 mg orally once daily. Drug-related adverse events resulted in dose modification, dose interruption, or permanent discontinuation of study treatment in 31 (69%) patients overall (18 [72%] FOLFOX and 13 [65%] FOLFIRI). Dose reduction or dose interruption of at least one of the chemotherapy components was observed in 52% of patients treated with FOLFOX and 65% of patients receiving FOLFIRI. A dose reduction of 5-fluorouracil due to AEs was necessary in 18% of administered cycles. 5-Fluorouracil administration was omitted in 8% of cycles. Oxaliplatin and irinotecan doses were reduced in 11% and 12% and interrupted in 11% and 5% of administered cycles, respectively. Actually, regorafenib had acceptable tolerability in combination with chemotherapy. The most frequent grade 3-4 AEs were: neutropenia (45%), Hand-Foot Skin Reaction (15%), diarrhea (10%), and hypophosphatemia (12%). Regarding pharmacokinetics, area under the curve (AUC) of irinotecan was significantly higher in cycle 2 (following regorafenib dosing) than in cycle 1 (before regorafenib dosing); the ratio of AUC values (cycle 2:cycle 1) was 1.28 (90% confidence interval [CI] 1.06 –1.54). Cmax of irinotecan was only slightly increased, and t1/2 was unchanged. For SN-38, AUC was significantly higher in cycle 2 than in cycle 1 (ratio 1.44, 90% CI 1.12–1.85), while Cmax was unchanged. In line with the known elimination pathways of platinum and 5-fluorouracil, no pharmacokinetic interaction with regorafenib was seen (10). The study from O'Neil et al. (11) was designed to show whether the addition of regorafenib to FOLFIRI improves PFS (over a placebo-FOLFIRI arm) when given as second-line therapy for patients treated initially with oxaliplatin and fluoropyrimidine-based therapy. The regorafenib/FOLFIRI schedule that was used was the one proposed by Schultheis et al. (10) (i.e. standard FOLFIRI with irinotecan 180 mg/m^2 plus regorafenib 160 mg daily from day 4 to 10). The study met its primary endpoint of demonstrating that the addition of regorafenib to FOLFIRI prolongs PFS compared to FOLFIRI alone with a HR of 0.72. When looking at tumor response, authors found that regorafenib (combined to chemo) provided more partial responses than placebo plus chemo (35% vs. 19%, p= 0.045). The combination was very tolerable, with little increase in toxicity compared to the control chemotherapy regimen. Of note, regarding the top-3 reported severe (gr. 3-4) AEs, neutropenia, diarrhea, and hypophosphatemia were reported in 41%, 15%,

and 14% of the patients, respectively (as compared to 30%, 5%, and 0% in the placebo group) (11).

- **There is room to combine regorafenib with a chemo triplet such as FOLFIRINOX (5-fluorouracil, irinotecan, oxaliplatin) on the following conditions:** controlling patients on *UGT1A* polymorphisms (at least UGT1A1), stepwise dose-escalation of irinotecan and regorafenib, mandatory granulocyte growth-factor injections.

**FOLFIRINOX or FOLFOXIRI:** A matter of dose of irinotecan and of 5-fluorouracil.

- **FOLFOXIRI** is a 60-minute infusion of **irinotecan at a dose of 165 mg/m^2**, and a 120-minute infusion of oxaliplatin at a dose of 85 mg/m^2 and a concomitant 120-minute infusion of Leucovorin at a dose of 200 mg/m^2 followed by a 48-hour continuous infusion of **fluorouracil to a total dose of 3200 mg/m^2**. Cycles are repeated every 14 days. This regime has been developed by Italian investigators in mCRC (2, 3).
- **FOLFIRINOX** is a 120-minute IV infusion of oxaliplatin at a dose of 85mg/m^2 on day 1, immediately followed by folinic acid 400 mg/m^2 (or calcium levofofolinate 200 mg/m^2) given as a 2-hour IV infusion, with the addition, after 30 minutes, of **irinotecan 180 mg/m^2**, given as a 90-minute intravenous infusion through a Y-connector immediately followed by **5-Fluorouracil 400mg/m^2 IV bolus then 2400mg/m^2** over 46 hours continuous infusion. Cycles are repeated every 14 days. This regime has been developed by french investigators in metastatic pancreatic cancer and in mCRC (11, 12).
- **We have selected FOLFIRINOX rather than FOLFOXIRI as a backbone of our experimental treatment because 1) french investigators are used to treat patients with such regimen, and because 2) the FOLFIRI-regorafenib that had been investigated by O'Neil et al (11) used the same irinotecan and 5-fluorouracil doses than the FOLFIRINOX regimen.**

**Why having chosen 48-week disease-control rate, rather than overall response rate as the primary objective of the phase II part of this FOLFIRINOX-R trial (see page 7)?** Overall response rate could have been the primary objective of this trial, as we are confident with the postulate that regorafenib is able to induce some additional tumour shrinkage to FOLFIRINOX backbone, but we are also cautious with that hypothesis. However, the 48-week disease-control rate includes not only the effect of

tumor responses that are awaited but also stable disease. In addition, this 48-week data cutoff (i.e.48-week disease-control rate) is also the median PFS (actually, 12.2 months) that had been reported in *RAS-mut* mCRC treated with the FOLFOXIRI-bevacizumab that we want to benchmark. To conclude, we think that the 48-week disease-control rate carries more valuable informations than overall response rate, as it captures the true effect of the addition of regorafenib to FOLFIRINOX.

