BACKGROUND AND RATIONALE	
Colorectal cancer (CRC) is a major cause of morbidity and mortality globally. More than 50% of patients can be expected to develop metastatic disease, and most of these patients will require palliative systemic therapy. The primary goal for patients who present with technically resectable liver metastases is definitely cure, with R0 resection as the primary goal. Consequently, any patient with limited liver and/or lung metastases should be considered a candidate for potential secondary resection as there are no criteria that allow physicians to distinguish between those patients for whom purely palliative treatment and those for whom potentially curative treatment is appropriate. Although survival times are slightly shorter for patients who undergo conversion therapy followed by surgery than for patients with initially resectable metastatic disease, they are far better than if resection is not carried out at all (1). As per ESMO guidelines, first-line therapy commonly involves the doublet (2-CT) regimens of 5-fluorouracil, folinic acid, and either oxaliplatin (FOLFOX) or irinotecan (FOLFIRI). The addition of targeted therapies, such as bevacizumab (a pure anti-angiogenic agent which binds circulating VEGF-A), cetuximab, and panitumumab, to FOLFOX or FOLFIRI may be helpful to some patients in improving tumor response and ultimately overall survival. The cytotoxic triplet (3-CT) FOLFOXIRI with or without bevacizumab may be an option in selected fit and motivated patients when cytoreduction (tumour shrinkage) is needed to undergo conversion therapy (1).
 
RAS mutations are found in about 50% of mCRC tumors. As recently rephrased by Modest et al. (2) these mutations exclude affected patients from epidermal growth factor receptor (EGFR)-directed therapy. Besides their negative predictive value, RAS mutations may also carry distinct prognostic information. Modest et al. (2) studied the prognosis by RAS status of a total of 1239 mCRC patients from five randomized trials studying 2-CT. Actually, PFS and OS were significantly influenced by molecular subgroups. Multivariate comparison of PFS and OS in patients with mutant tumors versus patients with non-mutated tumors revealed a negative prognostic effect of RAS mutations. Interestingly, the negative prognostic role of these mutations was consistently observed across different treatment regimens (subgroups of irinotecan- and oxaliplatin-treated patients as well as in bevacizumab- and non-bevacizumab-treated patients). Median PFS and OS were 10.3 vs. 9.5 months and 26.9 vs. 21.1 months in RAS-wildtype (and BRAF-wildtype) and RAS-mut patients, respectively (2). The TRIBE consortium reported that a 3-CT (FOLFOXIRI) combined with bevacizumab provided a significantly longer PFS (the primary end-point of the study) than did the 2-CT FOLFIRI plus bevacizumab (3, 4). In the subgroup of RAS- and BRAF-wild-type patients, those in the FOLFOXIRI plus bevacizumab group reported a median PFS of 13.7 months (95% CI, 10.1-18.1) compared with 12.2 months (95%CI, 9.5-14.4) in the FOLFIRI plus bevacizumab group (HR 0.85, 95%CI 0.55-1.3) (4).

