
Later on, the same group reported that FOLFOXIRI plus bevacizumab provided a significantly longer overall survival than the FOLFIRI plus bevacizumab group (HR 0.80, 95%CI 0.65–0.98;  $p=0.03$ ) (4). Looking at survival by RAS status, Cremolini et al. (4) reported that median OS was 37.1 months (95%CI, 29.7–42.7) in the RAS- and BRAF-wild-type subgroup compared with 25.6 months (95%CI, 22.4–28.6) in the RAS-mut subgroup (HR 1.49, 95%CI, 1.11–1.99). Interestingly, median PFS was 13.7 months (95% CI 10.1–18.1) in the RAS-wild-type subgroup treated with FOLFOXIRI plus bevacizumab, while PFS data were not given for the RAS-mut patients (4). However, for these RAS-mut patients, it was possible to estimate the median PFS (i.e. 9.4 months) from the Kaplan-Meier curve which was provided (4).

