### 3. Experimental plan

#### 3.1 Study design

This will be a prospective, Interventional, multicenter, open-label, uncontrolled phase I/II trial. 87 (18 phase I and 69 phase II including 6 patients treated at the RP2D during the phase I) patients will be included in several centers.

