#### Phase II

With a one-stage Fleming design,  $\alpha = 5\%$ ,  $\beta = 20\%$ ,  $p_0$  (the probability of inefficiency maximum) = 35% and  $p_1$  (the probability of minimum efficiency) = 50%, it would be necessary to include 65 evaluable patients (69 patients/ 5% non-evaluable patients).

The association can be considered sufficiently effective (reject null hypothesis) if there are at least 29 success (48 weeks disease control rate) out of 65 evaluable patients, the success rate is significantly greater than 35%.

The association can be considered insufficiently effective (reject alternative hypothesis) if there are 28 or less success out of 65 evaluable patients, the success rate is significantly lower than 50%.

In total, a maximum of 87 (=18 patients for phase I + 69 patients for phase II including 6 patients treated at the RP2D during the phase I) patients will be included.

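### The 48-week time point is justified by a 12.2-month RAS-mutated median that the protocol elsewhere gives as 9.4 months, and 29/65 is not significantly above 35% at the stated 5% level

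*Combined protocol and SAP*

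**What the plan says.** **The time point.** Section 1, in the paragraph on why 48-week disease control was chosen over response rate, first argues that disease control counts stable disease as well as response. It then adds that the 48-week cutoff "is also the median PFS (actually, 12.2 months) that had been reported in" RAS-mutated patients on FOLFOXIRI-bevacizumab, the regimen to be benchmarked. It concludes that the endpoint is the more informative one because "it captures the true effect of the addition of regorafenib to FOLFIRINOX".

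**The medians elsewhere.**
- Synopsis, background: "In the subgroup of RAS- and BRAF-wild-type patients, those in the FOLFOXIRI plus bevacizumab group reported a median PFS of 13.7 months". Section 1 gives the other arm of that wild-type subgroup: "compared with 12.2 months (95%CI, 9.5-14.4) in the FOLFIRI plus bevacizumab group".
- For RAS-mutated patients on FOLFOXIRI-bevacizumab, the synopsis explains that PFS was not reported but that "it was possible to estimate the median PFS (i.e. 9.4 months) from the Kaplan-Meier curve". Section 1 then highlights the benchmark: the median PFS in RAS-mutated "mCRC is 9.4 months (with FOLFOXIRI plus bevacizumab").

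**The rule.** Section 10.1 and the synopsis specify a one-stage Fleming design with alpha 5%, beta 20%, p0 = 35%, p1 = 50% and 65 evaluable patients (69 with 5% non-evaluable). With at least 29 successes the combination is sufficiently effective and "the success rate is significantly greater than 35"%.

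**The design and analysis.** Section 3.1 describes a "multicenter, open-label, uncontrolled phase I/II trial". Section 10.3 reports the 48-week rate as a percentage with a 95% CI, and PFS by Kaplan-Meier medians and rates with 95% CIs.

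**The concern.** The endpoint paragraph and the benchmark statement give different medians for the same population and regimen, and the larger one is used to justify the time point of the primary endpoint. If this is not settled before the results are known, two benchmarks are available and the more convenient one can be chosen afterwards.

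The decision rule raises a second, separate question. A report that repeats section 10.1 at exactly 29/65 would claim significance beside a 95% CI that contains the null value.

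A third question links the two: what may be said about the benchmark if the trial ends at or near its threshold.

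**Working it through.** **1. The medians side by side**

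| Population and regimen | Median PFS | Where |
|---|---|---|
| RAS-mutated, FOLFOXIRI-bevacizumab | 12.2 months, no source given | Section 1, endpoint paragraph |
| RAS-mutated, FOLFOXIRI-bevacizumab | 9.4 months, read from a curve, no CI | Synopsis background; section 1 |
| RAS/BRAF wild-type, FOLFIRI-bevacizumab | 12.2 months (9.5 to 14.4) | Synopsis background; section 1 |

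The first two rows cannot both be right.

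**2. The time point.** 48 × 7 = 336 days, and 336/30.4375 = 11.04 months. This equals neither 9.4 nor 12.2. With 28-day months it would be 12.0, which still does not match.

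**3. Reproducing the sample size.** n = [(z_α√(p0q0) + z_β√(p1q1))/(p1 − p0)]².
- One-sided 5%: [(1.645 × √(0.35 × 0.65) + 0.842 × 0.5)/0.15]² = 64.6, so 65. Then 65/0.95 = 68.4, so 69. Both stated figures reproduce.
- Two-sided 5% gives 81.7, so 82. The protocol does not state sidedness, but only the one-sided reading gives its n.

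**4. The rule of at least 29 out of 65.**
- Exact type I error: P(X ≥ 29 | 65, 0.35) = 0.069.
- Normal approximation: z = (0.4462 − 0.35)/√(0.35 × 0.65/65) = 0.0962/0.0592 = 1.625, one-sided p = 0.052. Equivalently, the normal cutoff is 22.75 + 1.645 × 3.845 = 29.08, which 29 just misses.
- Exact power: P(X ≥ 29 | 65, 0.50) = 0.839.
- Clopper-Pearson 95% CI for 29/65: 32.3% to 57.5%. One-sided 95% lower bound: 34.1%.
- For comparison, at least 30/65 has alpha 4.1% and power 77.1%. At n = 65 no cutoff meets both 5% and 80% exactly.

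**5. The 48-week rate implied by each median.** The documents give no such rate, so a curve shape must be assumed. With Weibull shape k and median m, S = 0.5^[(11.04/m)^k]; k = 1 is exponential.

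| Shape k | S at 48 weeks, m = 9.4 | P(X ≥ 29 of 65) at that rate |
|---|---|---|
| 0.8 | 45.5% | 60% |
| 1.0 | 44.3% | 53% |
| 1.5 | 41.4% | 34% |
| 2.0 | 38.4% | 18% |
| 2.5 | 35.5% | 8% |

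The last column takes no account of central review, which could only lower the probability. For m = 12.2, the exponential rate is 53.4%.

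The one-sided lower bound at 29/65 (34.1%) lies below every benchmark rate in the table, and the 95% CI contains all of them.

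**6. Counts that would exceed the benchmark.** Treating the benchmark as a fixed number, the exact one-sided 95% lower bound first exceeds it at 32/65 if the rate is 38.4%, 36/65 if 44.3%, and 37/65 if 45.5%.

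**The case against.** The best defence is that neither median was used to set p0, p1, n or the cutoff. Section 10.1 claims sufficient efficacy against an inefficacy limit of 35%, not superiority over FOLFOXIRI-bevacizumab, and a null below an active benchmark is legitimate. That stands: p0 = 35% is not at fault here, and success by a regimen equal to the benchmark is not a false positive against 35%.

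A reader might infer that 29/65 is the benchmark rate, so that meeting the go criterion can never show a gain. The documents do not support this. The roughly 44% rests on an assumed curve shape and a median read off a graph, and with a steeper curve it falls to 35.5%. Meeting the criterion also includes counts such as 36/65, which would exceed 44.3%. Only a result at or near 29/65 is uninformative about the benchmark.

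Nor do the documents say how 12.2 months entered the endpoint paragraph. A slip from the wild-type FOLFIRI-bevacizumab arm is plausible but not shown.

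The sentence about capturing regorafenib's true effect closes an argument for disease control over response rate; it is not an analysis claim. The context softens it, but an uncontrolled trial with no FOLFIRINOX-alone rate still cannot isolate that effect.

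Finally, a 9.4-month median PFS can already be addressed: investigator-assessed PFS with Kaplan-Meier estimates is a planned secondary analysis. The centrally reviewed binary rate is a poorer comparator. Section 7 sends only patients found progression-free to review, so review can only lower the rate, and the protocol does not say how the benchmark curve was assessed. This objection is accepted and shapes the fix.

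**Conclusion.** Two defects hold without any assumption about curve shape. First, the protocol gives 12.2 and 9.4 months for the same RAS-mutated benchmark, uses the former to justify 48 weeks, and 48 weeks (11.0 months) equals neither. Second, with alpha read as one-sided, 29/65 is not significantly greater than 35% at 5%: the exact type I error is 6.9% (5.2% by normal approximation). The exact 95% CI of 32.3% to 57.5% includes 35%. Power at 50% is 83.9%, above the planned 80%.

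The third conclusion is conditional. If PFS follows a Weibull curve with shape between 0.8 and 2.5, a 9.4-month median implies 35.5% to 45.5% at 48 weeks (44.3% if exponential). A result at or near 29/65 then does not by itself show improvement on the benchmark. From 36/65 upwards it could, under exponential PFS and with the benchmark taken as fixed. This equates 48-week disease control with 48-week PFS, although PFS runs from inclusion and the primary endpoint from start of therapy.

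**What to change.** Text changes only:

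1. **Section 1, endpoint paragraph.** Reconcile 12.2 with 9.4 months and cite the source of the figure kept. Delete the statement that 48 weeks is the median. Qualify the sentence about the effect of adding regorafenib, since the trial has no control arm.
2. **Section 10.1 and synopsis, statistical considerations.** State that alpha is one-sided and that the rule of at least 29/65 has exact alpha 6.9% and exact power 83.9%. Remove or qualify the claim of significance over 35% at 29/65.
3. **The analysis plan that section 10.3 says will be written before the database is closed.** State that 29/65 alone supports no claim of improvement over FOLFOXIRI-bevacizumab. Make any benchmark comparison with investigator-assessed Kaplan-Meier PFS (median and 48-week rate, each with 95% CI) against the curve that gave 9.4 months, and note that benchmark's own uncertainty. Do not use the centrally reviewed binary rate, or a fixed band of assumed rates, for this purpose.

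No patients are added, and n, p0, p1 and the decision rule stay as they are. The cost is a slightly less favourable stated alpha and a narrower permitted claim.
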